2.1.1.2 Planned/received treatment

- Intended/planned treatment is the first planned treatment reported in the DAR (e)CRF. For combination trial it is the combination of the first planned treatment reported in the DAR (e)CRF of each component of the combination.
- Treatment received is defined as:
 - (i) the treatment assigned if it was received at least once, or
 - (ii) the first treatment received when starting therapy with study treatment if the assigned treatment was never received.

Each patient will be classified into and analyzed consistently within one (and only one) treatment group/arm.

2.1.2 Assessment windows, baseline and post baseline definitions, missing data handling

2.1.2.1 Date of first administration of study drug

The date of first administration of study drug is derived as the first date when a nonzero dose of study drug was administered and recorded on DAR (e)CRF. For the sake of simplicity, the date of first administration of study drug will also be referred as *start of study drug*.

2.1.2.2 Date of last administration of study drug

The date of last administration of study drug is defined as the last date when a nonzero dose was administered and recorded on DAR (e)CRF.

2.1.2.3 Date of first administration of study treatment

The date of first administration of study treatment is derived as the first date when a nonzero dose of any component of study treatment was administered and recorded on DAR (e)CRF (i.e. earliest date between first LGX818 dose and first MEK162 dose for the dual combination and earliest date among first LGX818 dose, first MEK162 dose and first LEE011 dose for the triple combination). For the sake of simplicity, the date of first administration of study treatment will also be referred as *start of study treatment*.

2.1.2.4 Date of last administration of study treatment

The date of last administration of study treatment is derived as the last date when a nonzero dose of any component of study treatment (i.e. latest date between last LGX818 dose and last MEK162 dose for the dual combination and latest date among last LGX818 dose, last MEK162 dose and last LEE011 dose for the triple combination).

2.1.2.5 Last date of exposure to study treatment

Exposure to study treatment includes the exposure to any of the treatment component including any planned rest period between two administrations. As a consequence the last date

of exposure to a component of study treatment is the day before the first missed dose of any of the component:

- LGX818 once or twice daily (qd or bid) administration*: last date of exposure = last date of administration LGX818
- MEK162 twice daily (bid) administration: last date of exposure = last date of administration MEK162
- LEE011 once daily (3 weeks on, 1 week off schedule) administration: last date of exposure = last date of administration LEE011 + (number of last consecutive days of non 0 dose /planned consecutive days the patient should have taken the drug)*7

The last date of exposure to study treatment is the latest of the dates of last exposure of components of the combination or death date if earlier.

* LGX818 every other day (qod) administration: last date of administration LGX818 + 1 day.

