2.2 Analysis sets

For inclusion in any analysis set it is required that a patient has correctly consented and has received at least one dose of study treatment. For those incorrectly consented patients, they will be excluded from all analysis.

The following analysis sets which will be derived prior to database lock will be used.

Full Analysis Set

The FAS includes all patients who received at least one dose of LGX818 or MEK162 or LEE011. Patients will be classified according to the planned treatment regimen (dose, schedule, tablet variant). The FAS will be used for all listings of raw data. Unless otherwise specified the FAS will be the default analysis set used for all analyses.

Note that patients who were screened and are eligible but never started treatment will not be included in the FAS. This is considered as an acceptable deviation from the ITT principle in the context of the Phase I study in which safety is considered as a primary objective.

The FAS will be used for all listings of raw data. Unless otherwise specified the FAS will be the default analysis set used for all analyses. Patients will be analyzed according to the planned treatment regimen.

Safety Set

The safety set includes all patients who received at least one dose of LGX818 or MEK162 or LEE011, and have at least one valid post-baseline safety assessment. The statement that a patient had no AEs (on the AE eCRF) constitutes a valid safety assessment.

Patients will be classified according to treatment received (See Section 2.1.1.2).

Dose Determining Set (DDS)

The dose-determining set (DDS) includes all Phase Ib patients from the safety set who either completed a minimum exposure requirement and have sufficient safety evaluations or discontinued prematurely due to a dose limiting toxicity (DLT).

A patient is considered to have met the minimum exposure requirement if having received at least 75% of the planned combination doses (i.e. 21 out of 28 planned daily doses for QD or BID, 11 out of 14 planned doses for an every other day dosing schedule, and 16 days out of 21 days for 3 week on, 1 week off dosing schedule) of study treatment within the first Cycle of dosing. The length of a cycle is 28 days.

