3.3.1.2 Cumulative dose

The actual cumulative dose for each study drug is defined as the total dose for this study drug given during the study drug exposure and is expressed in mg. For patients who did not take any of the drug, the actual cumulative dose is by definition equal to zero.

The planned cumulative dose is defined as the total dose planned to be given during the study treatment exposure and is expressed in mg.

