3.3.1.3 Dose intensity and relative dose intensity

The dose intensity (DI) for patients with non-zero duration of exposure is defined as follows:

Planned dose intensity (PDI) (mg/day) = planned cumulative dose (mg) / planned number of days patient should have taken the drug (days)

Actual dose intensity (ADI) (mg/day) = actual cumulative dose (mg) / planned number of days patient should have taken the drug (days)

For patients who did not take any drug the ADI is (by definition) equal to zero.

ADI and PDI will be expressed in mg/day for LGX818, MEK162 and LEE011.

Relative dose intensity (RDI) = ADI (mg/day) / PDI (mg/day).

For patients who did not take any drug the actual RDI is (by definition) equal to zero.

The ADI and RDI will be summarized separately for each of the study treatment components by using the duration of the study treatment exposure, not the duration of each of the components.

The RDI for each of the study treatment components will be presented also with the following categories: <0.5, ≥ 0.5 to <0.75, ≥ 0.75 to <0.9, ≥ 0.9 to <1.1 and ≥ 1.1 .

Dose intensity for the first cycle or by cycle can be computed using cycle length definition (see Section 2.1.2.6) as exposure periods.

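### Triple combination: the LEE011 rest-week credit after the final dose enters every drug's planned dose, so fully adherent patients who stop all three drugs together before Day 28 of a cycle get an RDI below 1

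*SAP*

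**What the plan says.** Three rules act together.

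- **SAP 2.1.2.5** gives LGX818 (daily) and MEK162 a last exposure date equal to their last administration date. For LEE011 the date is "last date of administration LEE011 + (number of last consecutive days of non 0 dose", with that count divided by the planned consecutive days and multiplied by 7. It continues: "The last date of exposure to study treatment is the latest of the dates of last exposure of components of the combination", with the cap "or death date if earlier".
- **SAP 3.3.1.2**: "The planned cumulative dose is defined as the total dose planned to be given during the study treatment exposure".
- **SAP 3.3.1.3** defines RDI as ADI over PDI, both with the same day count as denominator, and has them summarised for each component "by using the duration of the study treatment exposure, not the duration of each of the components".

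The opening of 2.1.2.5 states two principles: exposure includes planned rest that falls between one dose and the next, and a component's exposure ends on the day preceding its first missed dose. Section 1.1 describes LGX818 and MEK162 as continuous; only LEE011 has an off week.

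**The concern.** The rest credit belongs to LEE011's schedule. Because the latest component date sets the study-treatment window, and that window sets every component's planned dose, the credit reaches two drugs for which no rest was ever planned. They are counted as having missed doses on days after permanent discontinuation.

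LEE011 is affected too when it stops in mid-course. The pro-rated credit then covers days on which LEE011 itself would have been due, and these are counted as planned but not taken.

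At stake is the descriptive account of how well the triplet was delivered. Section 3.6.9 names RDI and its categories as tolerability measures, and the final report includes triple-combination exposure summaries (Tables 14.4.1.1d and 14.4.1.4d). The distortion is largest for patients who stop early, who matter most when tolerability is read.

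**Working it through.** The SAP gives no worked RDI example, so there is no stated figure to reproduce. The check applies its rules directly.

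**Inputs**
- LEE011 credit (2.1.2.5): "number of last consecutive days of non 0 dose /planned consecutive days the patient should have taken the drug)*7".
- LEE011 planned consecutive days, 21 (2.2): "16 days out of 21 days for 3 week on, 1 week off dosing schedule".
- Cycle length (2.2): "The length of a cycle is 28 days".
- Assumptions: full adherence; LGX818, MEK162 and LEE011 stopped together, with LEE011 at its last scheduled dose if the stop falls in the off week; no death within the credit; unrounded credit unless stated.

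**Formulas**
- ADI and PDI share a denominator, so RDI = actual cumulative dose / planned cumulative dose.
- For a stop on day d of a cycle, let k = min(d, 21). Credit = (k/21) × 7 = k/3 days, counted from the last LEE011 dose.
- Study-treatment exposure ends at the later of the stop day and the last LEE011 day + k/3.
- For a continuous drug stopped on study day T, RDI = T / (day on which exposure ends).

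**LGX818 and MEK162**

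| Stop | Exposure ends | RDI |
|---|---|---|
| Cycle 1, d ≤ 21 | d + d/3 | d/(4d/3) = 0.75 |
| C1D25 | Day 28 | 25/28 = 0.893 |
| C1D28 | Day 28 | 28/28 = 1.00 |
| C2D21 | Day 56 | 49/56 = 0.875 |
| C3D21 | Day 84 | 77/84 = 0.917 |

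In mg, for a C1D21 stop on LGX818 200 mg QD and MEK162 45 mg BID: LGX818 4200/5600 = 0.75; MEK162 1890/2520 = 0.75.

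**Rounding.** The formula yields fractional dates and the SAP has no rounding rule. C1D21 is 0.75 in any case, because the credit is exactly 7 days. For earlier Cycle 1 stops, whole-day dates give exactly 0.75 only when d is a multiple of 3. A Day 5 stop gives 5/6 = 0.833 with the credit rounded down and 5/7 = 0.714 rounded up; a Day 4 stop rounded up gives 4/6 = 0.667. Rounding alone can therefore move a patient across the 0.75 category limit.

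**Categories.** With unrounded credit, RDI falls below 0.9 for stops on Days 1–25 of Cycle 1 and Days 15–22 of Cycle 2. Rounding shifts the edges: C2D14 is 42/46.67 = 0.900 unrounded but 42/47 = 0.894 rounded up. In Cycle 3 the unrounded minimum is 0.917, so no category changes from there on.

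**LEE011 itself, Cycle 1.** Up to Day 15 the credit ends by Day 20, within the 21 dosing days, so RDI = d/(4d/3) = 0.75. On Day 16 the window passes Day 21, giving 16/21 = 0.762; on Day 20, 20/21 = 0.952; on Day 21, 21/21 = 1.00.

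**Consistency within 2.1.2.5.** After 21 of 21 LEE011 days, the next dose is due on Day 1 of the next cycle, so the day preceding the first missed dose is Day 28. The 7-day credit agrees with that rule. For a stop on Day 9, the first missed dose is Day 10, so the rule gives Day 9, whereas the formula gives 9 + 3 = Day 12. The pro-rated part contradicts the section's own rule.

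**The case against.** The strongest reply is that nothing is planned to be given after permanent discontinuation, so a sensible programmer would get 1.00. The SAP does not say this. Section 3.3.1.2 ties planned dose to study-treatment exposure, and 3.3.1.3 explicitly rejects component-specific durations. The possibility of two codings shows that the text needs fixing; it does not remove the problem.

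Second, the SAP deliberately separates last administration (2.1.2.4) from last exposure (2.1.2.5). This stands for duration: counting the rest week after a completed 21-day course is a stated convention and fits the first-missed-dose rule. A reader might infer that duration is simply overstated and that the extension should be dropped altogether. The phrase limiting rest to the interval between doses leans that way, but the first-missed-dose rule leans the other way, so the documents do not settle it.

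Third, a reader might infer that every adherent triplet patient is affected, or that RDI is exactly 0.75 for any Cycle 1 stop by Day 21. Neither holds. A stop on Day 28 gives 1.00, death can shorten or remove the credit, continuing LGX818 and MEK162 through the credit removes the effect on them, and the exact value before Day 21 depends on rounding.

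Fourth, it is tempting to say that the triplet will look worse than the dual combination. Daily LGX818 with MEK162 has no such credit, but the SAP places dual and triple exposure in separate descriptive tables and plans no comparison of them.

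**Conclusion.** The point holds for RDI. As written, the rules give a fully adherent triple-combination patient who stops all three drugs together before Day 28 of a cycle an LGX818 and MEK162 RDI below 1: 0.75 on C1D21, about 0.75 for earlier Cycle 1 stops, 0.875 on C2D21 and 0.917 on C3D21. LEE011's own RDI is also too low for stops before Day 21 of a cycle, and the credit causing this conflicts with 2.1.2.5 itself.

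The reach is limited. RDI categories can change for Cycle 1 and some Cycle 2 stops but not from Cycle 3, and the SAP does not say how many patients stop that early. Only descriptive exposure and tolerability tables depend on it; the dose-determining set has its own exposure rule in 2.2, and no efficacy or DLT analysis uses RDI.

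The figures assume that the planned consecutive days are 21. If they meant days planned up to the stop, the credit would be a flat 7 days and early stops would fare worse (Cycle 1 Day 7: 7/14 = 0.50); the category effect would then reach early Cycle 3 (C3D1: 57/64 = 0.891). The C1D21, C2D21 and C3D21 values would not change.

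**What to change.** - **3.3.1.2 and 3.3.1.3:** count the planned cumulative dose of every component only over its own scheduled dosing days up to the date of last administration of study treatment (2.1.2.4), or death if earlier. Keep that as the common window for all components, so that stopping one drug early still lowers its RDI. Use the same window for the planned days in ADI and PDI, and amend the 3.3.1.3 sentence on duration to match.
- **2.1.2.5:** the rest-week credit may stay as a convention for duration of exposure after a completed 21-day LEE011 course. Remove the pro-rated credit for a stop before Day 21, or reconcile it with the first-missed-dose rule. If any fractional credit remains, state a rounding rule.

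With this change, a fully adherent patient has RDI 1.00 for all three drugs on any stop day. For a C1D21 stop, planned LGX818 becomes 4200 mg instead of 5600 mg and planned MEK162 1890 mg instead of 2520 mg.

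The cost is a small change to SAP wording and one derivation. Duration of exposure and RDI would then use slightly different end dates, which a table footnote should state. No dose or schedule is touched.

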2.1.2.6 Study day

The study day for all assessments **post**-treatment is calculated as the difference between the date of the event (e.g., visit date, onset date of an event, assessment date, disease progression, etc.) and the start of study treatment, plus one day. The first day of study treatment administration is therefore Study **Day 1**.

The study day for assessments **pre**-treatment is calculated as the difference between the date of the event (e.g., visit date, onset date of an event, assessment date, disease progression, etc.) and the start of study treatment. The day before start of study treatment administration is therefore Study **Day -1**. For the particular case of pre-treatment assessments performed on the day of first administration study day will be set to **Day 1**.

Unless specified otherwise, the study day is displayed in the data listings.

Cycle definition

The cycle number and day within cycle attributed to a visits or assessment will be derived according to the following rules:

- C1D1 (cycle 1 day 1) coincides with the start date of drug/treatment
- All pre-treatment assessments are displayed as Cycle 0 with a negative day (e.g., Day -1 for the day before the patient started treatment) or with day 1.
- Day 1 of a cycle corresponds to the day reported by investigator on the start of cycle log form.
- For all cycles but the last, the end date of a cycle is defined as the day before Day 1 of the following cycle as recorded on the cycle log form.
- The end date of the last cycle is when treatment administration is permanently discontinued at the latest of the following days:
 - Date of last administration

- 28 days after the first day of the last cycle or day of patient's death if earlier when date of last administration is not known
- All post-cycles assessments are displayed as follow-up and with, by analogy, Day 1 representing the first day after the end of the last cycle.

The duration (in days) of a cycle is defined as the cycle end date - cycle start date + 1.

Cycle number and day within cycle are computed to be displayed in listings only.

2.1.2.7 Baseline

Baseline is the last available and valid assessment performed or value measured within 14 days before the first administration of study treatment, unless otherwise stated under the related assessment section. Baseline can be the day before first treatment administration or the same day as first treatment administration if a pre-dose assessment/value is available (e.g., ECG, PK samples, samples for biomarkers).

If time is recorded for the first treatment dose and for a specific assessment performed the day of first dose, this assessment will be considered as baseline only if it is actually performed before the first dose, as checked using both times.

If time is not recorded, a specific assessment performed the day of first dose administration will be considered as baseline if, according to protocol, it should be performed before the first dose.

Patients with no data on a particular parameter before the first treatment administration will have a missing baseline for this parameter.

2.1.2.8 On-treatment assessment/event

An on-treatment assessment/event is defined as any assessment/event obtained in the time interval from the date of first administration of study treatment until the date of last administration of study treatment (i.e., including combination partner) + 30 days inclusive.

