3.6.7 Electrocardiograms

3.6.7.1 ECG data descriptive statistics

• Data from electrocardiogram will be listed, notable values will be flagged, and any other information collected will be listed. The frequency and percentage of patients with newly occurring qualitative ECG abnormalities will be tabulated. Shift table baseline to worst on-treatment result for overall assessments will also be summarized.

• Post-baseline values will also be categorized and tabulated to flag notable values according to the following rules:

Parameters	Criteria for ECG notable values	
QTcF (ms), QTcB (ms) and QT (ms)	New: > 450, > 480, > 500 ms	
	Increase from baseline > 30	
	Increase from baseline > 60	
HR (bpm)	Increase from baseline > 25% & to a value > 100	
	Decrease from baseline < 25% & to a value < 50	
PR (ms)	Increase > 25% to a value > 200	
QRS (ms)	Increase > 25% to a value > 110	

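### The on-treatment period starts on the calendar date of first dose, so a Day 1 pre-dose ECG used as baseline also enters the worst on-treatment ECG result it is compared with

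*SAP*

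**What the plan says.** SAP section 2.1.2.8 defines an on-treatment assessment or event as "any assessment/event obtained in the time interval from the date of first administration of study treatment until the date of last administration" plus 30 days, inclusive. Section 2.1.2.3 makes the start a calendar date: "the first date when a nonzero dose of any component of study treatment was administered and recorded on DAR (e)CRF".

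Section 2.1.2.7 says that baseline can fall on "the same day as first treatment administration if a pre-dose assessment/value is available (e.g., ECG, PK samples, samples for biomarkers"). ECG is the first example named. Where times are recorded, a same-day value is baseline only if it was "performed before the first dose, as checked using both times". Where they are not, the protocol schedule decides.

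Section 3.6.7.1 then states: "Shift table baseline to worst on-treatment result for overall assessments will also be summarized". The list of final tables in section 4.1.1 includes an ECG shift table, 14.3.6.2.3d, on the Safety Set for the triple combination.

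**The concern.** A shift table sets a value before treatment against values under treatment, so the two sets should not share an observation. Here they can. The date rule in 2.1.2.8 admits everything recorded on the day of first dose, including an ECG taken before the first dose. The baseline rule in 2.1.2.7 can select that same ECG.

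Two things are at stake in the ECG shift table. It may be unable to show any improvement in patients whose baseline was taken on Day 1. It may also report patients with no ECG after dosing as assessed and stable, when nothing is known about their ECG on treatment.

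**Working it through.** The SAP gives no figure to reproduce, so the check is a comparison of its rules.

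**Does another rule remove the overlap?**

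- The comparison of dose time and assessment time in 2.1.2.7 serves to choose the baseline. Section 2.1.2.8 has no matching check.
- Section 2.1.2.6 does not separate the values by study day: "For the particular case of pre-treatment assessments performed on the day of first administration study day will be set to" Day 1, which is also the study day of a post-dose value on that date.
- Section 2.1.2.6 labels pre-treatment assessments Cycle 0, which could separate them, but "Cycle number and day within cycle are computed to be displayed in listings only". The label does not govern summary tables.
- Where the SAP means post-baseline, it says so. Section 3.6.4 uses the worst post-baseline value for laboratory shifts, and 3.6.7.1 uses post-baseline values for ECG notable values. Only the ECG shift sentence uses the separately defined term on-treatment.

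**What does the literal rule do to the table?**

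Let B be the baseline, taken before dosing on Day 1, and W the worst result after the first dose. The literal rule records worst on-treatment = worse of (B, W), or B alone if W is missing. A post-dose rule records W. The SAP does not list the ECG result categories, so normal and abnormal are used here for illustration.

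| B | W | Literal rule | Post-dose rule |
|---|---|---|---|
| normal | normal | normal to normal | same |
| normal | abnormal | normal to abnormal | same |
| abnormal | abnormal | abnormal to abnormal | same |
| abnormal | normal | abnormal to abnormal | abnormal to normal |
| normal or abnormal | none | unchanged | missing |

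Only the last two rows differ. The number of patients shown differently is therefore (Day 1 baseline abnormal, all post-dose ECGs normal) + (Day 1 baseline, no post-dose ECG). The SAP gives neither count.

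**Can a patient without a post-dose ECG reach the table?**

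Yes. Section 2.2 admits a patient to the Safety Set on any valid post-baseline safety assessment, and a recorded statement of no adverse events is enough.

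**Do worsening percentages change?**

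No. The count of normal-to-abnormal shifts is the same under both rules, and section 3 takes percentages on the full group size unless otherwise specified.

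**The case against.** The strongest reply is that the SAP should be read as a whole. Section 2.1.2.6 calls a pre-dose assessment on the day of first dose pre-treatment, and 2.1.2.7 supplies timing rules to identify it, so a careful programmer would not also treat it as on-treatment. Section 2.1.2.8 covers events as well as assessments, and a date-based start is usual for adverse events. This makes the intended reading fairly clear, but it leaves the definition as written. The authors saw that Day 1 timing needed an explicit rule for baseline and gave none for on-treatment assessments.

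A second reply concerns the output. Table 14.3.6.2.3d is titled as a shift on notable values, whereas the sentence in 3.6.7.1 concerns overall assessments, and notable values are defined on post-baseline results. Section 1 also limits the final analysis to the outputs listed in section 4. This stands in part. The sentence in 3.6.7.1 is the only text that defines an ECG shift, so it is the apparent basis of the table, but the link is likely and not certain.

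A reader might also infer that an earlier, worse pre-dose ECG on Day 1 would be reported as worsening on treatment. The SAP does not support that. It would need several separate pre-dose ECG time points on Day 1, which the SAP does not show, and section 3 averages multiple measurements at one time point unless otherwise specified.

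**Conclusion.** The overlap is real on the text, and its effect is small. For patients whose baseline is a Day 1 pre-dose ECG, the literal rule leaves the improvement cells structurally empty and shows those without a post-dose ECG as evaluated and unchanged. Patients whose baseline comes from an earlier day are not affected.

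It would be too strong to conclude that the plan fails to describe ECG change on the combination. Worsening counts are intact, and the ECG notable-value table, which includes increases from baseline, uses post-baseline values, as do the laboratory shift tables. No percentage can be attached to the effect: the SAP gives no rate of abnormal baseline ECGs, no rate of return to normal and no count of patients without a post-dose ECG.

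The conclusion assumes that 2.1.2.8 is applied as written and that the shift sentence in 3.6.7.1 underlies Table 14.3.6.2.3d. The severity is minor: one descriptive safety table.

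**What to change.** Either of two edits is enough:

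- In 3.6.7.1, define the ECG shift as baseline to the worst post-baseline on-treatment value, in line with 3.6.4.
- In 2.1.2.8, state that assessments made before the first dose, including the value used as baseline, are not on-treatment. Timing would be judged by recorded time or, where none is recorded, by protocol schedule, as in 2.1.2.7.

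With either edit, keep the date-based start for adverse events and add a missing category to the shift table for patients with no post-dose ECG. It would also help to say in 3.6.7.1 whether Table 14.3.6.2.3d is the shift described there.

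The cost is a sentence of SAP text and one derivation flag that reuses the baseline timing logic. No new data are needed.
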